variable measured is the percentage ribcage, which is a measure of how much the belly and chest are individually contributing to breathing. Yoga emphasizes deep breathing which would involve both compartments which can be measured and used in a feedback loop to improve breathing.

[figure not shown]

Figure 3 Respiratory data displayed on iPad in real time

touch practitioner and the program coordinator for the yoga program at the Nemours Children's Hospital - Delaware.

Approach

Utilizing biofeedback will create two important changes. First, the yoga therapist would be able to update practice in real time. Objective data on breathing technique would allow correction in the moment so that a patient does not practice suboptimal breathing outside of the sessions and allow the therapist to adapt poses to ensure success. In turn, adequate practice at home could lead to a stronger treatment response. Secondly, the use of the biofeedback monitor would also allow for better introspection into the mind-body connection and improved adherence to practicing the skill.

Subjects: We will follow 20 subjects from the Integrated Pain and Wellness Program at Nemours Children's Hospital – Delaware. The program is embedded across multiple departments within the hospital system under the guidance of [name] (Behavioral Health Department) and [name] (Integrative Medicine Department). All subjects will be recruited in the latter 6 months of the project. Inclusion criteria: a) youth presenting for an initial evaluation within the Integrated Pain and Wellness Program, b) between 10 and 18 years old, c) prescribed yoga therapy as part of the treatment plan. Exclusion criteria include any medical condition precluding the use of yoga therapy.

The **feasibility** of the modified *pneuRIP* will be tested in this phase I proposal. The goals are to modify the existing *pneuRIP* software in the first 6 months then test it with a small cohort of subjects from the pain program in the second 6-month period. We will test the *pneuRIP* by recording respiratory data before and after individual yoga sessions, and before and after the entire regimen. Half of the subjects will be provided

Figure 2 PneuRIP shown with the two bands around the subject and iPad display of data

instructions to breathe deeply and synchronously between belly and chest while their breathing is recorded. The other half will additionally be provided biofeedback while they perform the same therapy.

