Data analysis: Numeric data will be summarized using mean (SD) or median (Interquartile range) as appropriate, and categorical data will be summarized using frequencies and percentages. Baseline and demographic characteristics will be compared using t-test, Mann-Whitney U test or Fisher exact tests as appropriate. A mixed effects repeated measures analysis of variance (ANOVA) will be used to compare the mean changes in breathing phase angle (degrees), labored breathing index (unit), blood oxygen level (%), respiratory rate (unit), pain acceptance scale, PROMIS pediatric pain interference scale, and PROMIS youth anxiety short form over time. Likert scale measures will be used as both numeric and categorical forms, thereby, a generalized mixed effects model will also be used to compare the changes in Likert scale over time. Model assumptions will be checked before analysis. All tests will be two-tailed at the level of significance of 0.05. Statistical software SAS, version 9.4, or R (version 4.05) will be used for the analysis.

Sample size and power: The primary goal is the change in breathing phase angle from baseline to after the yoga therapy regimen. In accordance with data from a previous study [29], the baseline mean (SD) phase angle is 40 (12) degrees, and after 8 weeks of yoga therapy we expect the phase angle to be 15 (9) and 30 (9) in the instructional + biofeedback group, and instructional alone group, respectively. A sample size of 8 subjects in each group can detect the above changes in phase angle with a power more than 80% at the level of the significance of 0.05. Assuming 25% attrition rate a sample size of 20 (10+10) subjects is planned for this study.

Potential problems, alternate strategies, benchmarks for success

Yoga is one of a few other therapies (cognitive behavioral therapy, physical and occupational therapy, massage, and/or medications) participants in this study may simultaneously be receiving. This makes it difficult to determine whether the breathing with biofeedback is the cause of improvement. However, this will be further examined in phase II with a controlled trial with a larger sample size.

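### The phase-angle model leaves its recordings, covariance and degrees of freedom unstated; a pooled-error version would test the primary contrast too liberally, and a baseline-adjusted two-value ANCOVA avoids this with more power

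*Protocol*

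**What the plan says.** The Data analysis paragraph is the same in the protocol and the SAP. It states that "A mixed effects repeated measures analysis of variance (ANOVA) will be used to compare the mean changes" in phase angle, the other respiratory measures and the questionnaire scores over time. It adds "Model assumptions will be checked before analysis" and "All tests will be two-tailed at the level of significance of 0.05", but names no covariance structure, degrees-of-freedom method, list of time points, or action if an assumption fails.

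Under Approach, the protocol plans "recording respiratory data before and after individual yoga sessions, and before and after the entire regimen". Specific aim 2 says that eight sessions are offered and that the pain measures are taken only before and after the whole regimen.

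Under Sample size and power, "The primary goal is the change in breathing phase angle from baseline to after the yoga therapy regimen". There "the baseline mean (SD) phase angle is 40 (12) degrees", and the expected end values are 15 (biofeedback) and 30 (instruction alone), each with SD 9. No within-child correlation is given.

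**The concern.** Phase angle may be recorded many times per child: eight post-session values plus a baseline make 9, and recordings before and after all eight sessions plus a baseline make 17. The primary question uses only the first and last.

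A classical repeated-measures ANOVA, or a mixed model whose only random term is a participant intercept, charges every contrast against one pooled within-child error. That is right only if all differences between two recordings have the same variance. End minus baseline spans the longest gap and includes the time point with the larger planned SD. If recordings far apart are less alike than neighbouring ones, or if baseline is more variable than the rest, the pooled error is too small for this contrast. Its p-value and confidence interval then overstate the evidence.

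As the plan is worded, whether this happens depends on a modelling choice that could be made after the data are seen.

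**Working it through.** **Inputs from the documents.** SD 12 at baseline and 9 at the end; expected arm difference at the end 30 - 15 = 15 degrees; 8 analysed per arm; two-sided 0.05.

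**Assumed, because the documents are silent.** The correlation between recordings, the path of the SD between 12 and 9, and the number of recordings in the model (2, 9 or 17).

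**The plan's own figure.** It says that "A sample size of 8 subjects in each group can detect the above changes in phase angle with a power more than 80" per cent. Comparing end values with SD 9: 15 / (9 x sqrt(2/8)) = 3.33, which gives 91.5% by the normal approximation and 87.2% by noncentral t. The claim reproduces.

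**Standard error of the primary contrast.** For one child,

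- true Var(end - baseline) = 12² + 9² - 2 x cov(baseline, end);
- pooled-error model Var = 2 x (mean variance - mean covariance), averaged over all recordings.

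Example A: 9 recordings, SD 12 then 9 throughout, equal correlation 0.5.

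- Mean variance = (144 + 8 x 81)/9 = 88.0.
- Mean covariance = (8 x 54 + 28 x 40.5)/36 = 43.5.
- Model Var = 2 x 44.5 = 89. True Var = 225 - 108 = 117.
- True SE / model SE = sqrt(117/89) = 1.15. Approximate level = 2 x (1 - Φ(1.96/1.15)) = about 9%.

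Example B: the same SDs, AR(1) with adjacent correlation 0.7.

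- Mean covariance = 32.1, so model Var = 2 x (88.0 - 32.1) = 111.8.
- True Var = 225 - 2 x 0.7⁸ x 108 = 225 - 12.5 = 212.5.
- Ratio = sqrt(212.5/111.8) = 1.38. Approximate level = 2 x (1 - Φ(1.96/1.38)) = about 16%.

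**Simulation with no true effect.** 8 per arm, 20,000 trials per setting, error df = 14 x (recordings - 1), correlation 0.5 to 0.8. Each cell gives the false-positive rate for the arm difference in end minus baseline, then true SE / model SE.

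| SD path and correlation | 9 recordings | 17 recordings |
|---|---|---|
| Gradual fall 12 to 9, equal correlation | 5-7%; 1.02-1.06 | 6-7%; 1.02-1.07 |
| Step to 9 after baseline, equal correlation | 9-10%; 1.15-1.19 | 9-11%; 1.17-1.23 |
| Gradual fall, AR(1) | 8-14%; 1.12-1.32 | 7-12%; 1.07-1.24 |
| Step, AR(1) | 12-19%; 1.25-1.47 | 11-17%; 1.22-1.41 |

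With only two time points the ratio is 1.00 and the level 5%, whatever the SDs or correlation.

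These ranges are not bounds. With 10 per arm, 16 recordings and slower decay (end-to-end correlation 0.1 to 0.7), the level was 15-22% with a gradual SD fall and 20-29% with a step.

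**Power of the two-value analyses** (8 per arm, difference 15, correlation 0.5).

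- Change score, which is the same test as group-by-time with two points: SD = sqrt(144 + 81 - 2 x 0.5 x 12 x 9) = 10.82; 15/(10.82 x 0.5) = 2.77 on 14 df; power 73%. It passes 80% only from a correlation of about 0.6.
- ANCOVA: residual SD = 9 x sqrt(1 - 0.5²) = 7.79; 15/(7.79 x 0.5) = 3.85 on 13 df. Simulation, which includes the cost of chance baseline imbalance, gives about 93%, with a false-positive rate of about 5%.

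**The case against.** The plan does not commit to the faulty model. A mixed model can carry unequal variances and decaying correlation, assumptions are to be checked, and leaving a structure unstated is not the same as choosing the wrong one. This stands. A reader might infer that the primary test is in fact a 10-18% test, but the documents do not support that as a property of the plan.

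A reader might also infer that the planning SDs contradict equal correlation. They bear on equal variance only. If the SD falls gradually and correlation is equal, the effect is slight (5-7%).

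The ratios are also easy to misread. A true SE 20-45% larger than the model SE means a model SE about 17-31% too small (1 - 1/1.20 and 1 - 1/1.45), not 20-45% too small.

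The primary goal names two time points, and no sentence says that all session recordings enter one model for it. The recording intervals are spelled out for the first session only, and the timeline figure is not available here. If just baseline and end are used, the problem disappears. The success criterion rests on the pain measures, which have two time points and are unaffected. All of this stands.

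It does not dispose of the point. The outcome is to be analysed over time, the recordings are planned around individual sessions, and nothing restricts the model to two of them. The assumption check has no stated consequence, and with about 16 to 20 children it has little power to detect unequal variance or decaying correlation.

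**Conclusion.** The point holds as a conditional one. The plan leaves open the recordings, covariance and degrees of freedom of the analysis that serves its primary goal, and one ordinary reading of its wording is anti-conservative for that contrast. Under that reading, with 9 or 17 recordings and 8 per arm, the nominal 5% level is about:

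- 5-7% with a gradual SD fall and equal correlation;
- 9-11% with an SD step after baseline and equal correlation of 0.5-0.8;
- 7-19% with AR(1) correlation of 0.5-0.8, where the true SE is up to about 45-47% larger than the model SE.

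Only the SDs at baseline and end come from the documents. The correlation and the SD path are assumptions, and other choices give more or less. The matter goes beyond missing detail because a better confirmatory analysis is available at almost no cost: it does not depend on the session-to-session covariance, and at the plan's SDs it has clearly more power than a change-score or group-by-time test.

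**What to change.** State in the SAP that the confirmatory phase-angle comparison uses one pre-specified baseline value and one pre-specified end-of-regimen value per child. Say which recording and breathing condition each comes from. Compare the arms by ANCOVA on the end value, adjusting for baseline. This holds 5% under the usual assumptions of normal errors with equal variance.

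Keep the session-by-session mixed model as supportive. List its time points, use a covariance that allows a separate baseline variance and correlation that decays with time (for example AR(1) plus a child effect), and use small-sample degrees of freedom such as Kenward-Roger. Name a simpler fallback in case this does not converge with about 16 children.

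The cost is a few sentences in the SAP, a little extra code, and somewhat wider intervals in the supportive model. Children without an end value do not contribute to the ANCOVA, but the sample-size paragraph already plans on 8 analysed per arm. No data or participants are added.

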bars. These metrics are computed directly on the *pneuRIP* hardware and are transmitted wireless to the application via Bluetooth Smart as BLE characteristics. On the front-end, the application will leverage modern web technologies including React framework and D3.js to render and animate the visuals.

Specific aim 2: Determine the immediate and cumulative impact of biofeedback on breathing by using the *pneuRIP* by measuring breathing pre- and post- individual, and multiple yoga sessions.

The **Rationale** for aim 2 is to determine the feasibility and utility of providing biofeedback on belly/chest breathing synchrony to participants in a clinical yoga setting for youth with pain. Subjects will be randomized into two groups: One will receive instruction on correct (synchronous) breathing technique, and the other will receive instruction and biofeedback. Youth enrolled within the Integrated Pain and Wellness Program at Nemours Children's Hospital - Delaware are referred to Integrative Medicine for yoga Therapy. As part of the program, youth are offered eight integrative therapy sessions at 30-60 minutes per session.

Group with instruction and monitoring. A group of 10 participants will be randomly selected and instructed to breathe in a synchronous manner utilizing the belly and chest muscles. The plethysmography bands will be attached to their chest and belly prior to the session. Their quiet breathing will be monitored prior to the first session. The protocol is shown in figure 5. They will be instructed by the yoga practitioner on how to synchronize belly and chest while breathing prior to beginning their session. For the initial 5 minutes of their yoga session, they will be asked to breathe synchronously. At the end of the first session, they will again be asked to breathe synchronously for 5 minutes. These breathing intervals will be continuously recorded by the *pneuRIP*.

Group with instruction and monitoring with biofeedback. A second group of 10 subjects will be selected and will follow the same protocol as the first group but will get biofeedback on an iPad while they are synchronously breathing.

Respiratory indices will be measured at the aforementioned intervals using the *pneuRIP*, pulse oximeter, and heart rate monitor. Standard measures of pain will be measured before and after the entire yoga regimen.

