Respiratory Biofeedback Sensor for Yoga Practice for Youth with Chronic Pain

NCT number: 05791435

1/3/22

Data Analysis:

Numeric data will be summarized using mean (SD) or median (Interquartile range) as appropriate, and categorical data will be summarized using frequencies and percentages. Baseline and demographic characteristics will be compared using t-test, Mann-Whitney U test or Fisher exact tests as appropriate. A mixed effects repeated measures analysis of variance (ANOVA) will be used to compare the mean changes in breathing phase angle (degrees), labored breathing index (unit), blood oxygen level (%), respiratory rate (unit), pain acceptance scale, PROMIS pediatric pain interference scale, and PROMIS youth anxiety short form over time. Likert scale measures will be used as both numeric and categorical forms, thereby, a generalized mixed effects model will also be used to compare the changes in Likert scale over time. Model assumptions will be checked before analysis. All tests will be two-tailed at the level of significance of 0.05. Statistical software SAS, version 9.4, or R (version 4.05) will be used for the analysis.

Sample size and power:

The primary goal is the change in breathing phase angle from baseline to after the yoga therapy regimen. In accordance with data from a previous study [29] the baseline mean (SD) phase angle is 40 (12) degrees, and after 8 weeks of yoga therapy we expect the phase angle to be 15 (9) and 30 (9) in the instructional + biofeedback group, and instructional alone group, respectively. A sample size of 8 subjects in each group can detect the above changes in phase angle with a power more than 80% at the level of the significance of 0.05. Assuming 25% attrition rate a sample size of 20 (10 + 10) subjects is planned for this study.

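### Name the primary phase-angle contrast as baseline-adjusted: the stated power reproduces for end values, but the endpoint is change from baseline, whose unadjusted power depends on a correlation the plan does not give

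*Protocol*

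**What the plan says.** The sample size paragraph, identical in substance in the protocol and the SAP, sets the endpoint: "The primary goal is the change in breathing phase angle from baseline to after the yoga therapy regimen". Its inputs are a starting value, "the baseline mean (SD) phase angle is 40 (12) degrees", and end values by group: "we expect the phase angle to be 15 (9) and 30 (9) in the instructional + biofeedback group, and instructional alone group, respectively". From these it concludes that "A sample size of 8 subjects in each group can detect the above changes in phase angle with a power more than 80" percent at a significance level of 0.05. Allowing for 25% attrition, 20 subjects are planned.

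The data analysis paragraph gives the model: "A mixed effects repeated measures analysis of variance (ANOVA) will be used to compare the mean changes in breathing phase angle (degrees", among other outcomes, over time. Tests are two-sided.

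The Approach section of the protocol plans "recording respiratory data before and after individual yoga sessions, and before and after the entire regimen". Specific aim 2 states that "Subjects will be randomized into two groups".

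Neither document gives an SD of change or a correlation between baseline and end values. Neither names a baseline covariate, a group-by-time term or any other between-group contrast as primary.

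**The concern.** The power inputs are SDs at single time points, while the endpoint is a change between two. The two match only if the analysis compares end values or if a correlation is supplied. As written, the same 16 to 20 subjects could be analysed by end values, by unadjusted change, or by end values adjusted for baseline, and these differ in power.

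With one baseline and one end value per subject, the group-by-time test in an unconstrained repeated measures ANOVA is the same as the unadjusted change comparison. So a natural reading of the stated model leads to the analysis that is weakest unless the correlation is fairly high. Leaving the contrast open in so small a trial also allows it to be chosen after the data are seen.

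**Working it through.** **Inputs from the documents.** Baseline SD 12; end SD 9 in both groups; end means 15 and 30, a difference of 15 degrees; 8 per group; two-sided 0.05; 10 + 10 recruited; 25% attrition.

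**Assumed input.** The baseline-to-end correlation ρ is not in the documents. Values of 0, 0.3, 0.5, 0.6 and 0.7 are used, taken as equal in both groups.

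**Step 1: reproduce the plan's figure.** For end values, the noncentrality is 15 / (9 × √(2/8)) = 15 / 4.5 = 3.33 on 14 df. The noncentral t gives 87.2% (91.5% by normal approximation). The claim of more than 80% reproduces.

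**Step 2: unadjusted change between two time points.** The variance of change is 12² + 9² − 2ρ(12)(9) = 225 − 216ρ. The noncentrality with 8 per group is 15 / (SD of change × 0.5). For example, at ρ = 0.5 the SD is √117 = 10.82 and the noncentrality is 15 / 5.41 = 2.77, giving 73.2%. The SD of change exceeds the end SD of 9 whenever ρ is below 144/216 = 0.667.

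**Step 3: end value adjusted for baseline (ANCOVA).** The residual SD is 9√(1 − ρ²), with N − 3 error df. Power was integrated numerically over chance baseline imbalance; simulation (200,000 runs each) agrees within 0.002.

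Power (%):

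| | ρ = 0 | 0.3 | 0.5 | 0.6 | 0.7 |
|---|---|---|---|---|---|
| SD of change | 15.0 | 12.66 | 10.82 | 9.77 | 8.59 |
| Unadjusted change, 8 + 8 | 46.1 | 59.7 | 73.2 | 81.5 | 90.0 |
| ANCOVA, 8 + 8 | 84.2 | 87.3 | 92.6 | 95.7 | 98.4 |
| Unadjusted change, 8 + 7 | 43.2 | 56.3 | 69.8 | 78.3 | 87.6 |
| ANCOVA, 8 + 7 | 80.9 | 84.3 | 90.3 | 94.1 | 97.5 |
| Unadjusted change, 10 + 10 | 56.2 | 70.8 | 83.4 | 90.1 | 95.8 |
| ANCOVA, 10 + 10 | 92.5 | 94.5 | 97.5 | 98.8 | 99.7 |

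The 8 + 7 rows are the plan's own attrition: 20 × 0.75 = 15. End values alone give 87.2% (8 + 8), 84.5% (8 + 7) and 94.1% (10 + 10), whatever ρ is.

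**Step 4: thresholds.** Unadjusted change reaches 80% at ρ = 0.58 with 8 + 8, 0.62 with 8 + 7 and 0.45 with 10 + 10. Subjects per group for 80%, in the order of the columns: 17, 13, 10, 8, 7 for unadjusted change and 8, 7, 6, 6, 5 for ANCOVA.

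**Step 5: other readings.** If a repeated-visit model with the same SD of change pools 42 to 210 error df, the threshold with 8 + 8 falls only to 0.54 to 0.52. If the claim refers to change within a group, power again depends on ρ: for instruction alone (40 to 30, n = 8, paired t) it is 37%, 49%, 61% and 81% at ρ = 0, 0.3, 0.5 and 0.7.

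**The case against.** The strongest reply is that no shortfall is shown. The power claim holds for end values, for the adjusted contrast at every ρ shown with 8 per group, and for unadjusted change once ρ is about 0.58. The plan does not name a two-time-point comparison of unadjusted change; a mixed model could treat baseline in other ways, including a common baseline mean. Against end values, the one basis that reproduces the stated power, adjustment gains only about 5 points at ρ = 0.5 (87.2% to 92.6%) and loses slightly below ρ = 0.30. The correlation is assumed throughout. This is also a feasibility study whose success is defined, under Potential problems, by pain measures.

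All of that is accurate, and it limits the point to a recommendation about the phase-angle goal. It does not remove it: the plan states a primary goal, a significance level and a power, and leaves open which analysis they belong to.

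A second objection also stands in part. The word baseline needs pinning down. Specific aim 2 has quiet breathing recorded before the first session and then synchronous breathing during which the biofeedback group already sees the display. A covariate taken from the latter could be affected by treatment. Figure 5, the data collection timeline, is not available here and may settle which recording is meant.

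**Conclusion.** The point holds as an improvement at almost no cost, not as an error in the sample size. With 8 per group, naming the baseline-adjusted contrast moves power from 46%–90% (unadjusted change) to 84%–98% over assumed correlations of 0 to 0.7. The adjusted contrast was ahead of unadjusted change at every correlation examined, from 0 to 0.9. It limits the dependence on the correlation but does not remove it. Against end values alone with 8 per group, it ranges from about 3 points worse at ρ = 0, through equality near 0.30, to 11 points better at 0.7.

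The figures assume normal data, a common slope and the same correlation in both groups. An expected end mean of 15 with SD 9 lies only 15/9 = 1.7 SD above zero, so a floor effect is possible if the index cannot be negative.

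**What to change.** In the data analysis paragraph of both documents, add:

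> The primary contrast is the between-group difference in end-of-regimen phase angle, adjusted for baseline phase angle (ANCOVA or the equivalent baseline-adjusted mixed model).

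State which recordings are the baseline and the end value. The baseline should precede instruction and biofeedback; the quiet-breathing recording before the first session is the natural candidate.

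In the sample size paragraph, restate the power:

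> With 8 per group, power is about 84% to 98% for a 15-degree difference (end SD 9, assumed baseline-to-end correlation 0 to 0.7, two-sided 0.05); with 8 and 7 it is about 81% to 97%.

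If unadjusted change is kept, give the assumed correlation or SD of change and the resulting power, for example 73% at 0.5 with 8 per group. If end values were the basis, say so and make the analysis match.

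The cost is two or three sentences in each document and one error degree of freedom. No subjects, visits or measurements are added.
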